4.1 Primary objective	
4.2 Secondary objectives	
5 STUDY ENDPOINTS.....	10
6 TIME SCHEDULE.....	10
7 STATISTICAL CONSIDERATIONS.....	11
8 INFORMED CONSENT.....	11
9 REFERENCES.....	11
Appendix.....	13

LIST OF ABBREVIATIONS AND DEFINITIONS OF TERMS

AE	Adverse Event
GPE	Global Perceived Effect
IC	Informed Consent
IL	Inferior Lateral
IM	Inferior Medial
NRS	Numeric Rating Scale
OKS	Oxford Knee Score
PPSP	Persistent Post-Surgical Pain
RFA	Radiofrequency Ablation
SL	Superior Lateral
SM	Superior Medial
ZOL	Ziekenhuis Oost-Limburg

ABSTRACT

Context: Management of chronic knee pain remains a challenge to the treating physician. Chronic knee pain can be the consequence of osteoarthritis but also of persistent post-surgical knee pain (PPSP). Conservative and surgical treatments may not always be the optimal solution in this diverse population, leading to a need for alternative treatment methods. A radiofrequency treatment of the genicular nerves is a not yet established but promising technique. It employs heat and an electrical field to target sensory knee nerve fibers in order to block them and alleviate chronic knee pain. This procedure is minimal invasive and has few adverse events. For these reasons it can be advantageous and fulfilling the unmet needs of these chronic knee pain patients warranting further research of its efficacy.

Objectives: This project has as primary objective the evaluation of treatment success of a conventional radiofrequency treatment of the genicular nerves in patients diagnosed with chronic knee pain due to osteoarthritis of the knee or PPSP at six weeks post treatment. Secondary objectives are evaluation of treatment effect at a third time point at the end of the inclusion period, subgroup analysis of treatment success based on indication to treatment, evaluation of subjective functional improvement and change in analgesics, estimation of the duration of effect of the treatment and adverse events.

Study Design: This study is a retrospective single-center cohort.

Setting/Participants: This study includes all patients treated with radiofrequency ablation in the multidisciplinary chronic pain center in Ziekenhuis Oost-Limburg, Campus Sint-Barbara between 1 September 2017 and 30 June 2020 with exclusion of patients with chronic widespread pain.

Main study endpoints: The main study outcome is the proportion of patients with a global perceived effect of at least 50% at 6 weeks post intervention. Secondary outcomes include reduction in pain intensity, measured by Numeric Rating Scale (NRS) at six weeks and at a third time point, global perceived effect at a third time point, subjective change in physical functioning, duration effect of the treatment, use of strong opioids, and adverse events.

PROTOCOL SYNOPSIS

Study Title	A retrospective single-center cohort study on patients with chronic knee pain treated with conventional radiofrequency of the genicular nerves.
Funder	ZOL Genk
Study Objectives	
Primary objective
 
• To evaluate treatment success of the conventional radiofrequency ablation at week 6 
Secondary objective
 
• Evaluation of treatment effect at a third time point at the end of the inclusion period• Subgroup analysis of treatment success based on indication to treatment• Evaluation of subjective functional improvement• Evaluation of change in analgesics• Estimation of the duration of effect of the treatment• Adverse events
Study Design	Retrospective single-center cohort study
Subject Population Key criteria for Inclusion and Exclusion:	
Inclusion Criteria
 
1. All patients with chronic knee pain who qualify for a conventional RF treatment of the genicular nerves 
Exclusion Criteria
 
1. Refusal to participate2. A negative diagnostic block with lidocaine 2% 1 ml of the three genicular nerves defined as less than 50% pain reduction3. Chronic widespread pain
Time	Patients treated with conventional RF treatment between 1 September 2017 and 30 June 2020.
Study endpoints	
1. Primary endpoint:
- Proportion of patients with treatment success at 6 weeks defined as GPE of $\geq 50\%$ compared to baseline.2. Secondary endpoints:
- Proportion of patients with treatment success at third time point defined as GPE of $\geq 50\%$ compared to baseline.- NRS reduction at week 6 and at the third time point- Subjective physical functioning at week 6 and at the third time point- Duration effect of the treatment defined as period with a GPE of $\geq 50\%$- Change in strong opioid use at week 6 and at the third time point- Safety: number/type of adverse events

1. BACKGROUND INFORMATION AND RATIONALE

Chronic knee pain is one of the most common disabling joint disorders in the global population.(1) Chronic knee pain can be the consequence of osteoarthritis but also of persistent post-surgical knee pain (PPSP). Osteoarthritis is an active degenerative disease that involves cartilage, subchondral bone and new bone formation leading to a considerable number of patients suffering from disabling symptoms such as chronic pain, stiffness and loss of function. The lifetime risk of developing symptomatic knee osteoarthritis is estimated to be ~45% based upon Johnston County Osteoarthritis Project data.(2)

Treatment strategies for chronic knee pain condition can be divided into surgical and non-surgical. When a conservative treatment fails to treat the symptoms, surgical techniques come to rescue. Total knee arthroplasty or an artificial replacement of the knee is the treatment of choice in multiple clinical situations of osteoarthritis. Despite being a successful treatment, comorbidities frequently hinder its application. Secondly, artificial joint replacement has unfortunately a limited longevity, and pain or discomfort after total knee replacement is frequent. (3-5) The percentage of patients that continues to report clinically significant pain and/or dissatisfaction after total knee arthroplasty mounts up to 19%-20%. (6-8) Residual pain has most commonly been associated with patellofemoral disorders, locating this pain largely in the anterior knee. (9) Due to this number of pitfalls a growing number of patients remain optionless facing disability, decrease in quality of life, extensive opioid consumption and/or polypharmacy. The groups of patients suffering from chronic knee pain including patients with comorbidities, non-geriatric patients and surgically treated patients with remaining knee pain have since the last decade been considered as potential candidates for treatment with radiofrequency ablation.

Radiofrequency treatment is a novel technique implemented on knee pain. This method targets the sensory innervation of the knee, leading to a decrease in the transmission of pain signals. The knee nerves presently targeted are the genicular nerves which are branches of the femoral, saphenous, obturator, common peroneal, tibial and sciatic nerve. This technique has little contraindications and few reported adverse events. As such it is a potential promising solution to persistent knee pain.

The first described conventional radiofrequency ablation of the genicular nerves is presented by Choi and colleagues in 2011. (10) In this double blind randomized trial patients showed significant improvement in pain and functionality scores in comparison with placebo. Since this first positive report, multiple investigations have explored and expanded the use of radiofrequency ablation towards pulsed radiofrequency and cooled radiofrequency treatment as alternatives to the conventional ablation. (11-13)

In the present retrospective cohort study we will analyze patients treated with this novel technique in our chronic pain center. The main aim of this study is to determine treatment success of radiofrequency ablation on patients with chronic knee pain. Furthermore, we aim to gain a better insight in demographics, indications, referring physicians, complications and adverse events that might be beneficial for organizing care for chronic knee pain patients.

2. STUDY DESIGN

2.1 Study design

This study is designed as a retrospective longitudinal cohort study of patients treated with a radiofrequency treatment of the genicular nerves in a single-center (ZOL, Genk) between 1 September 2017 and 30 June 2020. Each knee will be considered as a unique observation, and bilateral procedures were assessed specific to each knee treated. Data retrieved from the patient files will be collected at baseline, 6 weeks post-intervention and telephonically at a third time point which ranges from 6 weeks to 3 years after the procedure. The following demographic and clinical data will be collected at baseline: patient age, sex, NRS score, length of symptom duration, indication for the procedure, use of strong opioids, history of previous knee surgery and the referring physician. Strong opioid analgesics are defined as all opioids excluding tramadol and codeine.

Data collected at 6 weeks post-intervention will include: NRS, GPE, adverse events, and concomitant use of strong opioids.

Patient's data will be collected at a third time point. Written informed consent will be obtained by mail prior to contact by phone. After receiving informed consent, patients will be contacted by telephone and data will be gathered on the same variables as at 6 weeks post-intervention and on subjective functional outcome.

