4. STUDY OBJECTIVES

4.1 **The primary objective** of this study is to evaluate the treatment success of the conventional radiofrequency treatment of the genicular nerves in patients on patients diagnosed with chronic knee pain due to osteoarthritis of the knee or PPSP at six weeks post treatment. Treatment success is defined as a global perceived effect of at least 50% at measurement time point compared to baseline.

4.2 **The secondary objectives** are:

- Evaluation of treatment effect at a third time point at the end of the inclusion period
- Subgroup analysis of treatment success based on indication to treatment
- Evaluation of subjective functional improvement
- Evaluation of change in analgesics
- Estimation of the duration of effect of the treatment
- Adverse event

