5. STUDY ENDPOINTS

5.1 Primary endpoint:

Proportion of patient with treatment success at week 6 defined as a global perceived effect of $\geq 50\%$ compared to baseline.

5.2 Secondary endpoints:

- Proportion of patients with treatment success at third time point defined as a global perceived effect of $\geq 50\%$ compared to baseline.
- NRS reduction at week 6 and at the third time point.
- Subjective physical functioning at week 6 and at the third time point.
- Duration effect of the treatment defined as the period with a GPE of $\geq 50\%$.
- Change in use of strong opioids at week 6 and at the third time point.
- Safety: number/type of adverse events.

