7. STATISTICAL CONSIDERATIONS

Data will be presented as mean values and standard deviations or as median values and interquartile range (IQR) depending on the distribution of the data. The average post-treatment pain score will be estimated using linear mixed effects regression analysis using time since treatment as independent variable. We will use this multilevel approach as (most) patients contribute more than one post-treatment pain score to the dataset. This way, we will be able to estimate the 3 and 6 months effect of RF treatment. The statistical analysis will be performed using SPSS.

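### The unit of analysis is the knee in Section 2.1 but the patient in the primary endpoint, and Section 7 makes no allowance for paired knees in the success proportion

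*Combined protocol and SAP*

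**What the plan says.** Section 2.1 sets a general rule for the unit: "Each knee will be considered as a unique observation, and bilateral procedures were assessed specific to each knee treated".

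The success endpoint is worded differently wherever it appears:

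- Abstract: "The main study outcome is the proportion of patients with a global perceived effect of at least 50% at 6 weeks post intervention".
- Synopsis: "Proportion of patients with treatment success at 6 weeks defined as GPE of" at least 50%.
- Section 5.1: "Proportion of patient with treatment success at week 6 defined as a global perceived effect of" at least 50%.
- Section 5.2, third time point: "Proportion of patients with treatment success at third time point defined as a global perceived effect" of at least 50%.

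None of these mentions knees. Section 4.2 adds a further use of the same outcome: "Subgroup analysis of treatment success based on indication to treatment".

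Section 7 names one model: "The average post-treatment pain score will be estimated using linear mixed effects regression analysis using time since treatment as independent variable". The reason it gives for a multilevel approach is that most patients supply several pain scores after treatment. Two knees from one person are not mentioned, and the section gives no estimator or interval for the perceived-effect proportion.

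**The concern.** The plan foresees bilateral procedures but does not say how they enter its primary result. Read literally, Section 2.1 lets a bilateral patient count twice in something labelled a proportion of patients. Read the other way, Section 5.1 needs a rule for such patients (either knee, both knees, an index knee, or the mean of the two), and there is none.

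Two things are at stake. First, the reported success rate can change with the unit, and an open choice could be settled after the data are seen. Second, two knees from one person are unlikely to be independent. With positive correlation, an interval that ignores the pairing is too narrow. A comparison between indications can err in either direction, depending on whether bilateral patients usually have the same indication in both knees.

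**Working it through.** **Inputs.** The documents give no figure to reproduce: they state no sample size, expected success rate, number of bilateral patients or within-patient correlation. Everything below is therefore an assumption shown over a range. Let *f* be the share of patients treated in both knees, ICC the within-patient correlation of success, and *p* the success rate.

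**1. Weighting: per knee against per patient** (each patient weighted once, by the mean of that patient's knees).

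Shift = f(1 − f)/(1 + f) × (bilateral minus unilateral success).

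- The factor is 0.0452 at f = 0.05, 0.0818 at 0.10, 0.1615 at 0.30 and 0.1667 at 0.50. Its maximum is 0.1716, at f = 0.414.
- If the two kinds of patient differ by 10 to 20 points, the shift is 0.5 to 0.9 points at f = 5%, and 0.8 to 3.4 points over f = 10–50%. If they do not differ, it is zero.
- Example with f = 0.30, unilateral 55%, bilateral 40%:
  - per patient: 0.7 × 0.55 + 0.3 × 0.40 = 0.505
  - per knee: (0.7 × 0.55 + 0.6 × 0.40)/1.3 = 0.481

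**2. Patient-level rules.** Even with the same success rate in every knee, the rule for bilateral patients matters.

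P(both succeed) = p² + ICC × p(1 − p); P(either succeeds) = 2p − P(both).

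- p = 0.5, ICC = 0.5: both = 0.375, either = 0.625. With f = 0.20, success is 0.8 × 0.5 + 0.2 × 0.625 = 52.5% if either knee suffices, and 0.8 × 0.5 + 0.2 × 0.375 = 47.5% if both must succeed.
- p = 0.5, ICC = 0.3, f = 0.50: 58.75% and 41.25%.

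**3. Interval for a per-knee proportion.** This matters only if an interval is reported with knees treated as independent.

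Design effect DE = 1 + [2f/(1 + f)] × ICC; required widening = √DE − 1; actual coverage of the naive 95% interval = 2Φ(1.96/√DE) − 1.

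| f | ICC | DE | Widening | Coverage |
|---|---|---|---|---|
| 0.05 | 0.3 | 1.029 | 1.4% | 94.7% |
| 0.10 | 0.3 | 1.055 | 2.7% | 94.4% |
| 0.30 | 0.5 | 1.231 | 10.9% | 92.3% |
| 0.50 | 0.7 | 1.467 | 21.1% | 89.4% |

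A simulation agrees with the formula (beta-binomial pairs, true p = 0.45, 20,000 runs per setting). It used 50, 100 or 200 patients and f/ICC of 0.10/0.3, 0.30/0.5 and 0.50/0.7. Naive coverage was 88.7–94.6%, and coverage with patient-clustered robust variance was 94.1–94.9%. At 100 patients, f = 0.30 and ICC = 0.5, the figures were 91.8% naive and 94.4% clustered.

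**4. Difference between indications**, again with knees treated as independent, and with equal numbers of knees per group. Let *s* be the share of bilateral patients whose two knees have different indications.

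DE = 1 + [2f(1 − 2s)/(1 + f)] × ICC.

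| s (f = 0.30, ICC = 0.5) | DE | Coverage |
|---|---|---|
| 0 | 1.231 | 92.3% |
| 0.25 | 1.115 | 93.7% |
| 0.5 | 1.000 | 95.0% |
| 1 | 0.769 | 97.5% |

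The interval is too narrow when most bilateral patients have one indication in both knees, and too wide when most have different ones.

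**The case against.** The best defence is that Section 2.1 states one rule without exceptions, so it governs every outcome and the word patients in Section 5 is merely loose. A bilateral patient counting twice is then what the chosen unit implies. This is a fair reading, and the fix below adopts it. It does not remove the problem: the primary endpoint carries the other unit wherever it is stated, and paired knees still need an allowance.

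A second defence is that the plan contains no interval or test for the proportion, and that the indication analysis may be purely descriptive. Under-coverage is therefore conditional, as the working says. The absence of any analysis of the primary proportion is a separate gap. The effect of the unit on the point estimate does not depend on an interval being reported.

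Third, all the inputs are assumed and the larger effects need many bilateral patients. Half of all patients bilateral with a correlation of 0.7 is an upper illustration, and s = 1 is a bound. This stands and limits the claim about size.

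Finally, the multilevel model in Section 7 may well group by patient. It covers only the continuous pain score, so it does not reach the binary endpoint. A patient-level primary endpoint would also be defensible if the rule for bilateral cases were stated.

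**Conclusion.** The concern holds and should be fixed. The conflict between Section 2.1 and the endpoint wording is plain from the text, and Section 7 does not resolve it for the success proportion or for its analysis by indication. The practical size is unknown. It is near nil if few patients are bilateral, and over the assumed range of f = 10–50% it reaches a few percentage points in the estimate and a moderate loss of coverage in any interval that ignores pairing. A choice between patient-level rules could move the result further.

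**What to change.** 1. In the abstract, the synopsis and Section 5.1, define the primary endpoint as the proportion of treated knees with a perceived effect of at least 50% at week 6. Reword the third-time-point endpoint in the same way.
2. State treated knees as the denominator, and report the numbers of patients, treated knees and bilateral patients.
3. Add to Section 7 a 95% interval clustered on patient (logistic GEE or cluster-robust variance), with the same clustering for the indication subgroups.
4. Report a per-patient proportion as a sensitivity analysis, with each patient weighted once by the mean of that patient's knees.
5. Smaller points: state that the pain-score model is grouped by patient; summarise strong opioid use once per patient; ask the telephone questions on pain, effect and duration for each treated knee. In Section 2.2 the pain question refers to a single treated knee, and the effect and duration questions name none.

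The cost is wording, a patient identifier in the dataset and a few repeated telephone questions. The interval becomes about 3–21% wider than a naive one for f = 10–50% and ICC 0.3–0.7. In the simulated example with an assumed 100 patients, f = 30%, ICC 0.5 and 45% success, the half-width goes from 8.5 to 9.5 points.

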3.2.2 Exclusion Criteria

Patients will be excluded from participating in the study if they meet any of the following exclusion criteria:

1. Refusal to participate
2. A negative diagnostic block with lidocaine 2% 1 ml of the three genicular nerves defined as less than 50% pain reduction
3. Chronic widespread pain

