6. TIME SCHEDULE

Outcome / Time point	Baseline Consultation prior to inclusion	Diagnostic RF treatment	RF treatment	Consultation 6 weeks post treatment	Telephonic contact
Age	X				
Sex	X				
Duration of symptoms	X				
Previous knee surgery	X				
Referring physician	X				
Indication for treatment	X				
NRS	X			X	X
Strong opioid use	X			X	X
Chronic widespread pain	X				
NRS reduction $\geq 50\%$		X		X	X
Treating physician			X		
Subjective physical functioning score					X
GPE $\geq 50\%$				X	X
Adverse events				X	X
Informed consent					X

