APPENDIX

Description of the procedures:

Conventional radiofrequency treatment of the genicular nerves is performed in an outpatient setting. Patients are not required to stop anticoagulation prior to procedure. During the procedure the patient is monitored using pulse oximetry. No sedation is administered so the patient is able to communicate and report the stimulation adequate. The patient is placed in a supine position on a fluoroscopy table with the index knee flexed 10-15° by placing a cushion in the popliteal fossa.

Description of the procedure of the diagnostic nerve block

The eligible patients underwent diagnostic genicular nerve blocks with local anesthetic, which were performed under ultrasound guidance. The targets included the SL, SM and IM genicular nerves which pass periosteal areas connecting the shaft of the femur to bilateral epicondyles and the shaft of the tibia to the medial epicondyle. Lidocaine (1 mL of 2%) was injected at each target site. Responses were recorded as positive if the participant experienced a decrease in numeric pain scores of at least 50%. Patients with a positive response were included in the RF procedures.

Description of the procedure of conventional radiofrequency ablation

The procedure is performed under sterile conditions. A 100 mm long, 22 G straight RF cannula/introducer with a probe/electrode with a 5 mm active tip is used for the procedure. No corticosteroids are injected to decrease the risk of complications such as systemic effects and infection. The superomedial, the superolateral and the inferomedial genicular nerve are targeted using a high frequency linear ultrasound. The inferolateral genicular nerve is not targeted because of its proximity to the common peroneal nerve with its motor branches.

Superomedial genicular nerve

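### Section 7 promises the effect of RF, but an uncontrolled NRS change from one consultation score cannot separate that effect from regression to the mean, natural course and placebo response.

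*Combined protocol and SAP*

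**What the plan says.** Section 2.1 describes the design: "This study is designed as a retrospective longitudinal cohort study of patients treated with a radiofrequency treatment of the genicular nerves in a single-center". No comparator is described anywhere. The same section lists the data taken before treatment: "The following demographic and clinical data will be collected at baseline: patient age, sex, NRS score".

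In the section 6 schedule, the NRS row is marked under "Baseline Consultation prior to inclusion", at the 6-week consultation and at the telephone contact. It is not marked at the diagnostic visit. That visit carries only the yes/no item for a reduction of at least 50%.

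Section 5.2 lists the endpoint: "NRS reduction at week 6 and at the third time point". Section 7 fits a linear mixed model to post-treatment pain scores with time since treatment as the independent variable. It names no baseline term and concludes: "This way, we will be able to estimate the 3 and 6 months effect of RF treatment".

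Two further places concern the block. Section 3.2.2 excludes "A negative diagnostic block with lidocaine 2% 1 ml of the three genicular nerves defined as less than 50% pain reduction". The appendix says: "Responses were recorded as positive if the participant experienced a decrease in numeric pain scores of at least 50" per cent. Neither says which score the decrease is measured from.

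**The concern.** A single pre-treatment score taken when a patient presents for treatment may be above that patient's usual level. Part of any later fall would then happen without treatment. Chronic pain also has a natural course, and patients respond to having a procedure. With no comparator and one baseline score, the plan cannot separate these from the action of RF, and it does not mention any of them.

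What is at stake is the conclusion drawn from the NRS results. A fall in NRS at 3 or 6 months reported as the effect of RF would credit the procedure with change from all these sources. The background section itself cites a randomised comparison with placebo, so the distinction is familiar to the authors.

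**Working it through.** The documents give no NRS standard deviation, test-retest correlation or NRS entry threshold, and no figure to reproduce. Every number below rests on stated assumptions.

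**1. Regression to the mean from a given excess.** Let r be the correlation between two scores of the same knee. If consultation scores lie on average d points above the long-run mean, the expected fall without any treatment effect is (1 − r) × d. Assumed: r = 0.5 to 0.8 and d = 1 to 2 points.
- Smallest: (1 − 0.8) × 1 = 0.2 points.
- Largest: (1 − 0.5) × 2 = 1.0 points.

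**2. Regression to the mean from an implicit cut.** Suppose patients in effect enter only if the consultation score exceeds c. The expected fall is SD × (1 − r) × φ(a) / (1 − Φ(a)), with a = (c − mean)/SD. Assumed: mean 6, SD 2.
- c = 4, r = 0.8: 2 × 0.2 × 0.288 = 0.12 points.
- c = 5, r = 0.65: 2 × 0.35 × 0.509 = 0.36 points.
- c = 6, r = 0.5: 2 × 0.5 × 0.798 = 0.80 points.
- No selection on NRS: 0.

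Steps 1 and 2 together span about 0.1 to 1.0 points, or zero without selection. Natural course and placebo response come on top and are not sized here.

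**3. Would a pre-block score repair this?** If a second score played no part in selection, averaging it with the first would halve the figures in step 2 (0.06 to 0.40 points for c = 4 to 6). A pre-block score, if it is the reference for the 50% rule, does play a part: one that is high by chance makes a 50% fall easier to reach. A simulation of 2,000,000 draws with a true RF effect of zero shows the consequence. Each score is a true level plus independent error (mean 6, SD 2, correlation r). The block lowers pain by 2.5 points on average, and patients are kept if the post-block score is at most half the pre-block score. The spurious NRS reduction, in points, is:

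| r | cut c | consultation score | mean of both | pre-block score | consultation minus pre-block |
|---|---|---|---|---|---|
| 0.5 | none | 0.00 | 0.29 | 0.58 | −0.58 |
| 0.5 | 4 | 0.41 | 0.51 | 0.62 | −0.21 |
| 0.5 | 5 | 0.68 | 0.67 | 0.65 | 0.03 |
| 0.65 | none | 0.00 | 0.23 | 0.46 | −0.46 |
| 0.65 | 4 | 0.33 | 0.43 | 0.52 | −0.19 |
| 0.65 | 5 | 0.56 | 0.56 | 0.56 | 0.00 |
| 0.8 | none | 0.00 | 0.16 | 0.32 | −0.32 |
| 0.8 | 4 | 0.25 | 0.32 | 0.39 | −0.14 |
| 0.8 | 5 | 0.41 | 0.43 | 0.45 | −0.04 |

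The last column is the third minus the fifth. Under this model, averaging leaves the bias about the same or raises it. Other assumptions about how the errors of the pre-block and post-block scores are linked can give a halving or even a reversed sign. The consultation-to-block change in the last column does not track the spurious fall in the third, so it does not measure change without RF.

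**4. What the section 7 model estimates.** It uses post-treatment scores and time only. Its output is an average pain level at a given time, not a change from baseline and not a contrast with untreated knees.

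**The case against.** The other side is reasonable on several counts. Lack of a comparator is a known limit of any retrospective single-arm cohort, and the title declares the design. The eligibility criteria set no NRS threshold, and without selection on NRS the regression to the mean is zero. NRS reduction is secondary. The primary endpoint, GPE of at least 50% at week 6, is not calculated from the recorded baseline NRS.

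All of that stands, and it limits the size and reach of the point. It does not rescue the section 7 sentence, which goes beyond the design by naming the estimate as the effect of treatment.

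A reader might infer something stronger: that the block visit provides a second pre-RF score which the plan discards, and that averaging it in would halve the bias and cut the variance of the change by 25%. The documents do not support this. A pre-block score is only inferred from the percentage rule. The reference could be the consultation score, and absolute values may never have been filed. If the score exists, it belongs to the selection rule, as shown above. The 25% figure compares 2s²(1 − r) with 1.5s²(1 − r) and needs equal correlations. With an assumed 0.8 between the two baselines and 0.5 with follow-up, the variance falls only from 1.0s² to 0.9s². The bias, ignoring the block rule, falls from 0.5 to 0.9 − 0.5 = 0.4 of the excess.

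**Conclusion.** The point holds as a limit on interpretation. The NRS change in this cohort cannot be read as the effect of RF, and section 7 should not say that it can. The regression to the mean within it is about 0.1 to 1.0 NRS points if patients were implicitly selected on a high consultation score, and zero if not. The documents cannot say which, because the mean, SD, correlation and excess are all assumed.

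A reader might also infer that the observed reduction is mostly artefact, or that this arithmetic carries over to the primary GPE endpoint. Neither follows: no results are available, and the calculation applies only to differences from the consultation NRS.

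**What to change.** - **Section 7.** Replace the claim about the effect of RF with: *average pain score at 3 and 6 months after RF, and its change from the consultation score*. Because the model has no baseline term, say how that change is computed. Add that it includes regression to the mean and natural course, and that no share is attributed to RF without a comparator.
- **Sections 2.1 and 6.** State which score the 50% decrease after the block is measured from. If a separate pre-block NRS is on file, extract it.
- **Section 5.2.** Keep the consultation score as the main baseline. Report NRS reduction from the mean of the two scores only as a sensitivity analysis. Note that the pre-block score is part of the block selection rule, so the analysis is not a bias correction, and that the consultation-to-block change is not a clean estimate of change without RF.

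The cost is a few sentences, one extra chart field that may be missing in some or all files, and a more modest claim. The section 7 change is worth making whether or not a pre-block score is found.
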